Our recent study on the effect of carbamazepine on ENG concentrations in contraceptive implant users demonstrated clinically significant reductions in serum ENG concentrations with a median decrease of 61% (range 25.4-87.2) and 8/10 participants with concentrations <90pg/mL after the intervention.³ These findings added to the limited data on the pharmacokinetic interactions between cytochrome P-450 3A4 enzyme inducers (CYP-3A4) and the ENG contraceptive implant, and will likely lead to a change in the US Medical Eligibility Criteria (MEC) for Contraceptive Use. In the MEC, carbamazepine is lumped into a broad category of “Anticonvulsant therapy” that have known CYP-3A4 induction properties.⁴ This category also includes medications such as phenytoin, barbiturates, and topiramate. Many of these medications have well documented CYP-3A4 induction properties and

consistent pharmacokinetic effects with hormonal contraceptives.⁵ Topiramate is also a CYP-3A4 inducer, but has far less pharmacokinetic data to support that its induction properties have clinical implications. There are only two small published studies that investigated topiramate's pharmacokinetic effect on a combined oral contraceptive pill. Both studies found decreases in serum estrogen concentrations with concomitant topiramate use, but no significant pharmacokinetic effect of topiramate on norethindrone concentrations.^{6,7}

The data from the norethindrone studies suggest that topiramate's pharmacokinetic effect on hormonal contraceptives differs significantly from carbamazepine, yet the MEC provides identical recommendations for these medications. Because women with chronic migraines already have limited contraceptive options, differentiating the actual interactions is crucial.

Research design and methods

Outcome Measure: Serum etonogestrel concentrations measured at baseline and then repeated after participants reach three titrated doses of topiramate:

- Visit 2 = 100mg per day
- Visit 3 = 200mg per day
- Visit 4 = 400mg per day

Description of Population to be Enrolled:

We aim to enroll subjects between 18-45 years old based on the following criteria:

Inclusion Criteria: Healthy women, who have had an ENG implant for 12-36 months at the time of enrollment and will maintain their implant during the study without modifications.

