After the participant has been consented, we will perform a blood draw to obtain whole blood and serum. Appropriate blood samples will be sent to the University of Colorado Clinical Laboratory for a comprehensive metabolic panel. A blood sample for serum will be centrifuged on location and the serum collected for storage in our -80°F freezer. For participants that meet our laboratory exclusion criteria, we will ultimately measure a serum baseline ENG concentration from the serum collected at the enrollment visit. The research team will then follow-up the comprehensive metabolic panel to determine final eligibility based on the criteria discussed above. Eligible participants will then be given the options of either returning to our clinic to pick up the first course of the study medication or have this first course mailed to them via FedEx.

Participants will then begin a 6 week titration schedule of topiramate to a max dose of 200mg bid by the final week. Women with chronic migraines are typically treated with a dose of 100 or 200mg/day, which will be achieved in the third and fourth week of titration, respectively. The maximum recommended dose of topiramate for treatment of epilepsy is 400mg/day, which will be achieved in the sixth and final week of titration. All participants will return at the end of the third week of the topiramate titration schedule. We will then draw blood from participants at this third week visit. An appropriate blood sample will be sent to the University of Colorado Clinical Laboratory for topiramate

measurement as a measurement of compliance. Serum obtained from this blood draw will be again stored in our -80°F freezer for eventual serum ENG concentration measurement. Participants will also undergo screening for adverse events (AEs) and serious adverse events (SAEs) at this follow-up. Any participant experiencing an SAE will be removed from the study. Participants will then be given the next course of the study medication to continue the titration schedule.

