All participants will return at the end of the fourth and sixth weeks to undergo identical study procedures as described for the third week visit. The final course of the study medication will be provided at the fourth week visit to continue the titration schedule through to the conclusion of the study. A topiramate level will again be measured as a measure of study compliance and serum stored for eventual serum ENG concentration measurement. At the conclusion of enrollment, all stored serum samples will be de-identified and assigned a random identification number (three letters) so that the laboratory is blinded to the timing of samples. We will then ship all samples to a Merck® laboratory for serum ENG concentration measurement. Batch analysis will be performed using a liquid chromatography mass-spectrometry method that has been previously validated. Participants will serve as their own controls for this study.

Abrupt cessation of topiramate therapy has been associated with increase in seizures in patients taking the medication for epilepsy. It is unclear if this risk is present in healthy individuals taking topiramate, but we will have participants undergo a gradual withdrawal of topiramate over 1 week after the final blood draw (end of 6 weeks). Participants will be given this withdrawal regimen at the final blood draw visit and undergo down-titration of their topiramate dose over the course of 1 week. Participants who choose to discontinue their participation early will contact the PRA or study physician for a custom down-titration schedule or abrupt discontinuation in the case of serious adverse events.

All participants will be required to use either a back-up non-hormonal method of birth control or abstain from intercourse during the study and for 4 weeks after the last dose of topiramate. Topiramate has a half-life of 21 hours, and thus, will be eliminated within 1 week of the last dose, but we will allow another 3 weeks of buffer to ensure that the ovulation has not occurred and that the contraceptive effect of the implant has reinitiated before recommending resuming unprotected intercourse.

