All study visits will occur at the Comprehensive Women's Health Clinic in Lowry. This is our Family Planning site for both clinical and research visits. All consent and enrollment processes will be conducted in a private clinic room and interested participants will be allowed as much time as needed to review the consent and ask any questions regarding the consent and study procedure.

Treatment:

Etonogestrel contraceptive implant - All participants will have had an ENG implant for 12-36 months at the time of enrollment and will maintain their implant during the study without modifications.

Topiramate – Participants will undergo a 6 week titrated regimen of oral topiramate to reach a maximum dose of 400mg per day, followed by a 7-day withdrawal titration schedule, and 4 week abstinence/back-up period:

Week 1: topiramate PO 25mg daily

Week 2: topiramate PO 25mg twice daily

Week 3: topiramate PO 50mg twice daily

Week 4: topiramate PO 100mg twice daily

Week 5: topiramate PO 150mg twice daily

Week 6: topiramate PO 200mg twice daily

Week 7: withdrawal titration schedule – topiramate PO 100mg twice daily for 2 days, 100mg daily for 2 days, 50mg daily for 2 days, 25mg daily for 1 day

Week 8 – 11: abstinence/backup period

Data Analysis Plan

For this study, non-inferiority was defined as a change in serum ENG concentration that would not result in concentrations below the threshold for ovulatory suppression. We chose a non-inferiority limit of 30% because this level of decrease from the median published levels (157-207pg/mL) does not cross the probably threshold for ovulatory suppression (90pg/mL). Based on the variance findings from our carbamazepine study (SD = 67.7), we performed a sample size calculation with an alpha level of 0.05 and a beta of 0.9 for our non-inferiority limit of 30%. We used a higher beta cut-off to account for the use of a statistical sample size calculation based on a normal distribution when serum ENG concentrations has a known non-normal distribution. This calculation resulted in a sample size of 27 women. We will enroll up to 53 women to account for a potential 49% drop-out/non-compliance rate, which accounts for an expected 30% intolerance rate for topiramate doses >200mg/day. Given that this will be a repeated measures study of non-parametric data, we will use a Friedman test for our analysis. We will use a p-value of <0.05 as a cut-off for statistical significance.

Citations

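### Run on all four measurements, the Friedman test leaves women without a valid 400 mg sample out of the migraine-dose aim, although their 100 and 200 mg samples are to be drawn and assayed

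*Combined protocol and SAP*

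**What the plan says.** The Outcome Measure is "Serum etonogestrel concentrations measured at baseline and then repeated after participants reach three titrated doses of topiramate", namely 100, 200 and 400 mg/day. Aim 1 concerns the migraine doses (100-200 mg/day) and Aim 2 the epilepsy dose (400 mg/day). The Rationale describes migraine prevention as the drug's main current use.

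The Data Analysis Plan names a single analysis: "Given that this will be a repeated measures study of non-parametric data, we will use a Friedman test for our analysis". It does not say which measurements enter the test.

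On timing, the Study Design section says of 100 and 200 mg/day: "which will be achieved in the third and fourth week of titration, respectively". Blood is drawn at the ends of weeks 3, 4 and 6. The Treatment section first exceeds 200 mg/day with "Week 5: topiramate PO 150mg twice daily". On assay, the Study Design section says "We will then ship all samples" for ENG measurement.

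On loss, the Data Analysis Plan says: "We will enroll up to 53 women to account for a potential 49% drop-out/non-compliance rate, which accounts for an expected 30% intolerance rate", the 30% being tied to doses above 200 mg/day.

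On early stopping, the Study Design section says: "Participants who choose to discontinue their participation early will contact the PRA or study physician for a custom down-titration schedule", or abrupt discontinuation for a serious adverse event. The same section removes from the study any woman with a serious adverse event. It also says that all participants return at the end of week 6, and "A topiramate level will again be measured as a measure of study compliance". Nothing states what becomes, in the analysis, of samples drawn before a woman stops or is removed.

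**The concern.** The standard Friedman test ranks the measurements within each woman, so each woman must have a value at every level. With four levels, a woman who gives baseline, 100 and 200 mg samples but no valid 400 mg sample contributes nothing, not even to the migraine-dose question. The plan itself forecasts that many women will be in this position, and it places the forecast loss after both migraine-dose draws.

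What is at stake is Aim 1. It carries no requirement that a woman also tolerate more than 200 mg/day, yet a four-measurement test would answer it only in women who did. It would also set aside assayed data. If the choice of women is not fixed in advance, it will be made once the results are known.

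**Working it through.** **Inputs (Data Analysis Plan).** Required number 27; total drop-out and non-compliance 49%; intolerance above 200 mg/day 30%, included in the 49%; enrolment ceiling 53.

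**The plan's own figure.** 27 / (1 - 0.49) = 27 / 0.51 = 52.9, rounded up to 53. This matches. In reverse, 53 × 0.51 = 27.0.

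**Order of events.** Baseline draw; 100 mg/day draw, end of week 3; 200 mg/day draw, end of week 4; first dose above 200 mg/day, week 5; 400 mg/day draw, end of week 6. Intolerance that first shows above 200 mg/day therefore falls after the Aim 1 samples are drawn.

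**Behaviour of the test.** In simulated data with 43 women, 16 of them lacking the fourth value, a four-measurement Friedman test gave no result until the incomplete rows were deleted, which left 27. A three-measurement test (baseline, 100, 200) kept all 43.

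**Women with baseline, 100 and 200 mg samples.** Assume that 27 is the number of complete series and that 53 are enrolled. The documents do not say how the 49% divides, so two splits are shown:
- Losses add: other loss = 0.49 - 0.30 = 0.19.
- Losses multiply: share surviving other loss = 0.51 / 0.70 = 0.729.

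All other loss is placed before the week-4 draw. At equal SD of change, the reduction in the standard error of a dose-versus-baseline mean is 1 - √(27/n).

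| Timing of intolerance stops | Split | n with Aim 1 samples | Unused | Reduction in SE |
|---|---|---|---|---|
| All after the 200 mg draw | multiply | 53 × 0.729 = 38.6, about 39 | 12 | 1 - √(27/39) = 17% |
| All after the 200 mg draw | add | 53 × 0.81 = 42.9, about 43 | 16 | 1 - √(27/43) = 21% |
| Half before it | multiply | 53 × 0.729 × 0.85 = 32.8, about 33 | 6 | 1 - √(27/33) = 10% |
| Half before it | add | 53 × (1 - 0.19 - 0.15) = 35.0, about 35 | 8 | 1 - √(27/35) = 12% |
| All before it | either | 27 | 0 | 0% |

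**If 27 is not the number of complete series.** Non-compliance is not defined, and non-compliant women may have all four samples. If all other loss is of that kind and those women are analysed, 53 × 0.70 = 37 series are complete out of 53 with Aim 1 samples. That leaves 16 unused, and the reduction is 1 - √(37/53) = 16%.

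**If the SDs differ.** Let c be completers, n all women with Aim 1 samples, and k the SD of change in the added women divided by that in completers. With equal means, the gain vanishes when (c + (n - c)k²)/n² = 1/c, that is, k = √(1 + n/c). With c = 27, k runs from √(1 + 33/27) = 1.49 to √(1 + 43/27) = 1.61.

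**The case against.** The strongest reply is that the plan never commits to one test on four measurements. The aims are separated by dose, and a Friedman test on baseline, 100 and 200 mg would fit the text and keep these women. That stands, and it is why the point is conditional. The plan does not specify that test either, so the matter is open.

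Second, the Study Design section has all participants return at week 6. A woman who could not tolerate the higher doses might still attend, and a test by visit would keep her. The point assumes that women who stop do not attend, or that a sample taken off dose does not count as a 400 mg measurement. The Outcome Measure, which ties Visit 4 to 400 mg/day, favours the second assumption but does not settle it.

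Third, a Friedman test yields a p-value and no standard error, so the gain belongs to the estimate that would replace it. This is correct. Whether a Friedman test can address non-inferiority at all is a separate question and lends no weight here.

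Fourth, a completer set compares all doses in the same women. That is a good reason to show it, but a weak one for restricting Aim 1.

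A reader might infer three stronger things that the documents do not support:
- That the trial falls short of its planned size. It does not: 53 was chosen so that 27 remain.
- That Aim 1 would be biased in a known direction. Nothing in the documents says how ENG change differs between women who tolerate the higher doses and women who do not.
- That the plan discards samples from women who stop. It is silent on this, and it ships all samples.

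**Conclusion.** The point holds as a conditional one. The only named analysis needs complete blocks, the plan forecasts substantial loss after the Aim 1 samples are drawn, and no rule says which women enter each aim's analysis. On the four-measurement reading, Aim 1 is restricted to women who tolerated the higher doses and loses precision that the collected samples could give.

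The size is modest and rests on assumptions: a standard error 17-21% smaller for the replacement estimate if all intolerance loss follows week 4, 10-12% if half precedes the 200 mg draw, and none if all does. The plan's tie of the 30% to doses above 200 mg/day makes the first case the closest to its own forecast. The figures further assume enrolment at the ceiling of 53, 27 as the number of complete series, and a common SD of change. This is a worthwhile, inexpensive improvement and not a fault that defeats the trial. Confidence is medium, because the intended use of the test and the split of the 49% are not stated.

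**What to change.** Add to the Data Analysis Plan:

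- For each dose, a within-woman comparison with baseline that uses every woman with a baseline sample and a valid sample at that dose. This can be a paired analysis of log ENG, or a mixed model with visit as a fixed effect and woman as a random effect.
- A confidence interval for the percentage change at each dose, read against the plan's 30% limit.
- A statement that valid samples drawn before a woman stops or is removed are kept, and a rule on whether a week-6 sample taken off dose counts as a 400 mg measurement.
- The number of women analysed at each dose.
- The four-visit Friedman test in completers, as a sensitivity analysis.

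The cost is wording in the analysis plan. No further participants, visits, samples or assays are needed. The downside is that the number and mix of women differ by dose, so comparisons between doses should also be shown in completers.

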Official Title: The effect of topiramate on etonogestrel concentrations in contraceptive implant users

NCT Number: NCT03335163

Document date: 12/19/2017

Principal Investigator: [name] and [name]

Proposal Narrative

Objective: To evaluate the pharmacokinetic effect of concomitant topiramate therapy on etonogestrel (ENG) contraceptive implant use.

Specific Aims:

1. To evaluate the drug-drug interaction between doses of topiramate used for treatment of migraines (100-200mg per day) and the ENG contraceptive implant.
2. To evaluate the drug-drug interaction between doses of topiramate used for treatment of epilepsy (400mg per day) and the ENG contraceptive implant.
3. To characterize whether any pharmacokinetic reductions in serum ENG concentrations reach below the level needed to maintain ovulation suppression (<90pg/mL).

Rationale:

Topiramate is an anti-epileptic drug initially used for treatment of partial-onset seizures and primary generalized tonic-clonic seizures. However, its main use currently is for migraine prevention: topiramate is considered a first-line treatment for migraine prophylaxis, along with B-blockers and valproate.¹ The majority of patients afflicted by chronic migraines are reproductive age women, most of whom need reliable contraception.² Few women with chronic migraines are candidates for estrogen-containing contraceptive methods. We have recently cared for several reproductive age women taking topiramate and have found no evidence supporting or contraindicating the etonogestrel (ENG) contraceptive implant for birth control, and only scant evidence regarding drug-drug interactions between topiramate and norethindrone-containing combined oral contraceptives. As topiramate is a Pregnancy Class D drug, definitive evidence of any potential decreased efficacy of the implant is imperative. Conversely, reassuring evidence of stable ENG levels will broaden the contraceptive options for women using topiramate.

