Exclusion Criteria: We will exclude women who are taking any known cytochrome P-450 3A4 enzyme inducers or inhibitors. We will also exclude women with a body mass index (BMI) <18.5, as underweight women may have altered metabolism. We will not have an upper BMI cut-off as studies have shown that overweight and obese women have equivalent metabolism and efficacy with the ENG contraceptive implant.^{8,9}

We will also exclude women with any hepatic or renal dysfunction as determined by a comprehensive metabolic panel. For purposes of this study, liver function tests will be evaluated and evidence of hepatic dysfunction will be defined as an ALT >52 or AST >39, which are beyond the reference range of normal values used by the University of Colorado clinical laboratory. Renal function will be assessed by a serum creatinine and a value >1.2 will be evidence of renal dysfunction as this is greater than the reference range used by the University of Colorado clinical laboratory.

We will also assess for any history of hepatic or renal disease to screen for diseases such as hepatitis, cirrhosis, kidney transplant, etc.

We will also exclude women with a low serum bicarbonate on screening serum electrolytes due to potential increased risk for side-effects from topiramate. We will use a cut-off of bicarbonate <21 for purposes of this study as this value is outside the reference range for the University of Colorado clinical laboratory.

Study Design

We will conduct a prospective, non-inferiority study to evaluate the pharmacokinetic effect of topiramate on serum ENG levels in contraceptive implant users. We will enroll healthy women using an ENG implant for at least 12 months and no greater than 36 months. Our exclusion and inclusion criteria are detailed as above. Interested women will undergo a phone screening prior to scheduling an enrollment visit. At the enrollment visit, potential participants will have their vital signs checked in the form of a pulse and blood pressure and will have their height and weight measured for purposes of calculating a body mass index. We will review each potential participants past medical history and current medications to ensure study eligibility. If interested participants meet our non-laboratory inclusion and exclusion criteria, then they will undergo informed consent in a private clinic room.

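### The trial is declared and sized as non-inferiority with a 30% limit, but its only named analysis, a Friedman test at p<0.05, never uses that limit

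*Combined protocol and SAP*

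**What the plan says.** The Study Design section states the type of trial: "We will conduct a prospective, non-inferiority study to evaluate the pharmacokinetic effect of topiramate on serum ENG levels". The Data Analysis Plan gives the meaning, namely that "non-inferiority was defined as a change in serum ENG concentration that would not result in concentrations below the threshold for ovulatory suppression", and then the limit: "We chose a non-inferiority limit of 30% because this level of decrease from the median published levels (157-207pg/mL) does not cross" the presumed ovulation-suppression threshold of 90 pg/mL. The sample size of 27 is calculated for that limit, with alpha 0.05, a 'beta' of 0.9 (read here as 90% power) and an SD of 67.7.

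The analysis itself takes two sentences: "Given that this will be a repeated measures study of non-parametric data, we will use a Friedman test for our analysis", and "We will use a p-value of <0.05 as a cut-off for statistical significance".

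The Specific Aims pose three questions. Aim 1 concerns "doses of topiramate used for treatment of migraines (100-200mg per day) and the ENG contraceptive implant". Aim 2 concerns "doses of topiramate used for treatment of epilepsy (400mg per day) and the ENG contraceptive implant". Aim 3 asks whether any reduction takes ENG below 90 pg/mL. ENG is measured four times in each woman: at baseline and at 100, 200 and 400 mg per day.

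The document contains no confidence interval, no test against the 30% limit, no dose-versus-baseline contrast and no rule for declaring non-inferiority.

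**The concern.** A non-inferiority claim needs evidence that the true fall is smaller than the limit. The Friedman null hypothesis is that ENG is the same at all visits, which is a different question. The plan does not say how either outcome of that test would be read.

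Both readings carry a risk. A non-significant p-value may be taken as reassurance when the data were only too noisy to show a fall. A significant p-value may be taken as evidence against the implant when every fall lies well inside the limit. The rationale section wants the result to inform contraceptive choice for women on topiramate, so either misreading matters. In addition, the alpha and power stated for the 30% limit belong to a test that the plan does not contain.

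**Working it through.** **1. The plan's own sample size.** Inputs from the Data Analysis Plan: SD 67.7, limit 30%, alpha 0.05, power 0.90. The reference level is not given; 182 pg/mL, the midpoint of 157-207, is assumed. The two-group formula with one-sided alpha gives

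n = 2 × (1.645 + 1.282)² × 67.7² / (0.30 × 182)² = 26.3, rounded up to 27.

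This matches the plan, and 27/(1 − 0.49) = 52.9 gives the 53 to be enrolled. The match is not unique: two-sided 0.05 gives 32.3 (33) at 182 and reaches 27 only for a reference of about 199-203. It does indicate that the sizing rests on a comparison with the limit, which the analysis section lacks.

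**2. Friedman without any variance assumption.** With n = 27 and k = 4 visits, let every woman fall in the same order. The rank sums are 27, 54, 81 and 108, so

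χ² = 12/(27 × 4 × 5) × (27² + 54² + 81² + 108²) − 3 × 27 × 5 = 486 − 405 = 81 on 3 df, p = 1.9e-17.

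The percentages do not enter. Falls of 2/4/6% and of 50/60/70% give the same result, and so do rises in the reverse order.

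**3. Illustration with noise.** n = 27, 20,000 runs, independent visit noise on the log scale. The SD of a woman's log change is assumed to be 0.20, 0.30, 0.40 or 0.57. The last is a rough value from the carbamazepine range of 25.4-87.2% in 10 women: (ln 0.746 − ln 0.128)/3.078 = 0.573. The margin test passes if mean − 1.706 × SD/√27 > ln 0.70.

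| True falls at 100/200/400 mg | Result | SD 0.20 | 0.30 | 0.40 | 0.57 |
|---|---|---|---|---|---|
| (a) 10/20/30% | Friedman non-significant | 0% | 0.1% | 5% | 32% |
| | Margin test passes at 400 mg | about 5% | about 5% | about 5% | about 5% |
| (b) 5/10/15% | Friedman significant | 90% | 55% | 33% | 17% |
| | Margin test passes at all doses | >99.9% | 94% | 76% | 43% |
| (c) 5/10/35% | Friedman significant | 100% | 100% | 99.6% | 88% |
| | Margin test passes at 200 mg | 100% | 99.6% | 94% | 72% |
| | Margin test passes at 400 mg | 0% | 0.2% | 0.5% | 1.1% |

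In (a) the 400 mg fall lies on the limit, yet with noisy data the Friedman test is often silent. In (b) all falls are inside the limit, yet with precise data it is usually significant. In (c) Aims 1 and 2 have opposite answers, and the Friedman test returns one p-value for both.

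**4. The threshold.** A 30% fall reaches 90 pg/mL from a baseline of 90/0.70 = 128.6. From the published medians it reaches 0.70 × 157 = 109.9 and 0.70 × 207 = 144.9. The limit therefore protects a woman at the median, but not one who starts below 128.6. A mean ratio alone does not cover the plan's own definition of non-inferiority.

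**The case against.** The best defence is that ENG concentrations are skewed and measured repeatedly, and that a Friedman test is a standard choice for such data. That justifies a rank method but not this hypothesis: a signed-rank test or Hodges-Lehmann limit against 0.70 is also rank-based and does use the limit.

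It is also fair to say that the Friedman test is not blind to the size of the fall. Its power rises as the fall grows relative to within-woman noise, and the identical statistics of 81 need all 27 women to fall in the same order. That example shows what is possible, not what is likely. The precise statement is that the test uses ranks only and never the 30% limit.

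The 32% in row (a) depends on the noise model and should carry little weight. The 0.57 reflects how differently women responded to carbamazepine, and such differences would probably persist across doses. If the total SD stays at 0.57 but the visit noise contributes only 0.20 (assumed), non-significance in (a) drops to about 0.3-0.4%, and significance in (b) rises from 17% to about 46%. The main danger is then a significant p-value with falls inside the limit.

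Finally, Aim 3 is worded descriptively, and a missing sentence on counts would by itself be a minor gap. It matters more here because the same threshold defines non-inferiority.

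**Conclusion.** The concern holds and must be fixed. Followed exactly, the plan cannot show or refute the non-inferiority it sets out to test, and it cannot separate the migraine doses from the epilepsy dose. This conclusion follows from the text and from the assumption-free calculation giving 81 in both cases. It does not rest on the simulated percentages, which depend on assumed SDs and on independent visit noise, nor on the assumed reference of 182 pg/mL. The paired data that the trial will collect can answer the question; only the specified analysis cannot.

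**What to change.** Rewrite the analysis sentences of the Data Analysis Plan, before the assay results are seen, to state the following.

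- **Primary analysis, per dose.** Take the within-woman log ratio of ENG (dose/baseline). Conclude non-inferiority at that dose only if the lower confidence limit of the geometric mean ratio exceeds 0.70. If a rank method is preferred, use a signed-rank/Hodges-Lehmann limit against 0.70.
- **Alpha.** State the sidedness. A one-sided 95% limit fits the 27 under the assumption above, but the plan does not settle it, so the sponsor should choose.
- **Aims.** Aim 1 requires both 100 and 200 mg to pass, Aim 2 requires 400 mg, and an overall claim requires all three.
- **Analysis set.** Say who is analysed at each dose, above all at 400 mg, since the plan expects 30% intolerance above 200 mg/day and 49% loss overall.
- **Aim 3.** Report the number and proportion of women below 90 pg/mL at each visit, including baseline, with an exact 95% interval (for example, 0/27 gives 0-12.8%). State whether this count is part of the non-inferiority criterion or descriptive.
- **Friedman test.** Keep it as a descriptive secondary result.

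The cost is wording only. If 67.7 is the SD of the within-woman change in pg/mL (the plan does not say) and there is no true change, a paired test against the limit with 90% power needs 11-20 women at one-sided 0.05, or 13-24 at one-sided 0.025. These ranges cover references of 207 down to 157 pg/mL and normal or t calculations. All lie within the planned 27.
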